7. MANAGEMENT OF COMMON OR EXPECTED ADVERSE EXPERIENCES

The severity of adverse events will be determined using the grading system outlined in the NCI Common Terminology Criteria for Adverse Events Version 4.03 (CTCAE), as it best fits the diagnostic terminology used in naming the event at the site clinical level.

SOFOBUVIR/LEDIPASVIR OR RIBAVIRIN (ADVERSE EVENTS IN COMMON)

CTCAE SOC	Adverse Event	Grade Description	Criteria for Modification of Intervention	Procedure for Modification
General disorders and administration site conditions	Fatigue	1 – Relieved by rest	Grade 3 or if requested by study participant	Intervention can be withheld for up to 5 days. If there is no resolution, the case will be discussed with the medical monitor and the intervention may be discontinued.
		2 – Not relieved by rest; limiting instrumental ADL		
		3 – Not relieved by rest; limiting self-care ADL		
Nervous system disorders	Headache	1 – Mild pain	Grade 3 or if requested by study participant	Intervention can be withheld for up to 5 days. If there is no resolution, the case will be discussed with the medical monitor and the intervention may be discontinued.
		2 – Moderate pain; limiting instrumental ADL		
		3 – Severe pain; limiting self-care ADL		
Gastrointestinal disorders	Nausea	1 – Loss of appetite without alteration in eating habits	Grade 3 or if requested by study participant	Intervention can be withheld for up to 5 days. If there is no resolution, the case will be discussed with the medical monitor and the intervention may be discontinued.
		2 – Oral intake decreased without significant weight loss, dehydration or malnutrition		
		3 – Inadequate oral caloric or fluid intake; tube feeding, TPN, or hospitalization indicated		
Gastrointestinal disorders	Vomiting	1 – 1-2 episodes (separated by 5 minutes) in 24 hours	Grade 3 or if requested by study participant	Intervention can be withheld for up to 5 days. If there is no resolution, the case will be discussed with the medical monitor and the intervention may be discontinued.
		2 – 3-5 episodes (separated by 5 min) in 24 hours		

		3 - ≥ 6 episodes (separated by 5 min); tube feeding, TPN or hospitalization indicated		

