		5 - Death		
Investigations	Blood bilirubin increased	1 - >ULN - 1.5x ULN	Grade 3-4	Intervention can be withheld for up to 5 days. If there is no resolution, the case will be discussed with the medical monitor and the intervention may be discontinued.
		2 - >1.5-3x ULN		
		3 - >3-10x ULN		
		4 - >10x ULN		
Investigations	Lipase increased	1 - > ULN-1.5x ULN	Grade 3-4	Intervention can be withheld for up to 5 days. If there is no resolution, the case will be discussed with the medical monitor and the intervention may be discontinued.
		2 - >1.5-2x ULN		
		3 - >2-5x ULN		
		4 - >5x ULN		

Ribavirin

CTCAE SOC	Adverse Event	Grade Description	Criteria for Modification of Intervention	Procedure for Modification
Blood and lymphatic system disorders	Anemia	1 - Hgb <LLN-10g/dL	Grade 2, modifications to dosage	Grade 2: see dosage adjustment procedure in section 5.1.iii
		2 - Hgb <10-8g/dL		
		3 - < 8g/dL	Grade 3-5: permanently discontinue ribavirin	Grade 3-5: ribavirin will be permanently discontinued. Subject experiencing Grade 3 or 4 will continue the study intervention and follow study
		4 - Life-threatening consequences; urgent intervention indicated		

		5 – Death		evaluations as detailed in section 6.1
Blood and lymphatic system disorders	Hemolysis	1 – Laboratory evidence of hemolysis only (e.g. DAT, Coombs', schistocytes, decreased haptoglobin)	Grade 2: modifications to dosage Grade 3-5: permanently discontinued	Grade 2: see dosage adjustment procedure in section 5.1.iii Grade 3-5: intervention will be permanently discontinued.
		2 – Evidence of hemolysis and $\geq 2g/dL$ decrease in Hgb		
		3 – Transfusion or medical intervention indicated		
		4 – Life-threatening consequences; urgent intervention indicated		
		5 – Death		
Hepatobiliary disorders	Hepatic failure	3 – Asterixis; mild encephalopathy; limiting self care ADL	Grade 3-5	Intervention can be withheld for up to 5 days. If there is no resolution, the case will be discussed with the medical monitor and the intervention may be discontinued. Grade 5: Intervention will be permanently discontinued
		4 – Moderate to severe encephalopathy; coma; life-threatening consequences		
		5 – Death		

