Immune system disorders	Allergic reaction	1 – Transient flushing or rash, drug fever < 38 degrees C; intervention not indicated	Grade 3-5 or if requested by study participant	Intervention can be withheld for up to 5 days. If there is no resolution, the case will be discussed with the medical monitor and the intervention may be discontinued. Grade 5: Intervention will be permanently discontinued
		2 – Intervention indicated; responds promptly to symptomatic treatment; prophylactic medications indicated for ≤ 24 hours		
		3 – Prolonged (not rapidly responsive to symptomatic medication); recurrence of symptoms following initial improvement; hospitalization indicated for clinical sequelae		

		4 – Life-threatening consequences; urgent intervention indicated		
		5 - Death		
Immune system disorders	Anaphylaxis	3 – Symptomatic bronchospasm, with or without urticarial; parenteral intervention indicated; allergy-related edema/angioedema; hypotension	Grade 3-5	Intervention can be withheld for up to 5 days. If there is no resolution, the case will be discussed with the medical monitor and the intervention may be discontinued. Grade 5: Intervention will be permanently discontinued
		4 – Life-threatening consequences; urgent intervention indicated		
		5 – Death		
Gastrointestinal disorders	Pancreatitis	2 – Enzyme elevation or radiologic findings only	Grade 3-5	Intervention can be withheld for up to 5 days. If there is no resolution, the case will be discussed with the medical monitor and the intervention may be discontinued. Grade 5: Intervention will be permanently discontinued
		3 – Severe pain; vomiting; medical intervention indicated (e.g. analgesia, nutritional support)		
		4 – Life-threatening consequences; urgent intervention indicated		
		5 – Death		
General disorders and administration site conditions	Irritability	1 – Mild; easily consolable	Grade 3 or if requested by study participant	Intervention can be withheld for up to 5 days. If there is no resolution, the case will be discussed with the medical monitor and the intervention may be discontinued.
		2 – Moderate; limiting instrumental ADL; increased attention indicated		
		3 – Severe abnormal or excessive response; limiting self care ADL; inconsolable		
Skin and subcutaneous tissue disorders	Pruritis	1 – Mild or localized; topical intervention indicated	Grade 3 or if requested by study participant	Intervention can be withheld for up to 5 days. If there is no resolution, the case will be

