8. CRITERIA FOR INTERVENTION DISCONTINUATION

The intervention will be withheld/discontinued for specific grades of adverse effects as detailed in section 7. Additionally, the intervention will be discontinued if the subject meets criteria for the following reasons:

Virologic failure, defined as:

Breakthrough: HCV RNA \geq LLOQ after having previously had HCV RNA $<$ LLOQ, while on treatment, confirmed with 2 consecutive values (note: second confirmation value can be posttreatment), or last available on-treatment measurement with no subsequent follow up values, OR

Rebound: > 1 log₁₀IU/mL increase in HCV RNA from nadir while on treatment, confirmed with 2 consecutive values (note: second confirmation value can be post-treatment), or last available on-treatment measurement with no subsequent follow up values, OR

Nonresponse: HCV RNA persistently \geq LLOQ through 8 weeks of treatment, OR

Relapse: HCV RNA \geq LLOQ during the posttreatment period having achieved HCV RNA $<$ LLOQ at end of treatment, confirmed with 2 consecutive values or last available posttreatment measurement

Pregnancy: If a woman becomes pregnant or a male's female partner becomes pregnant while on-study, the subject will be required to instruct investigators immediately. If he/she is in Arm 1, he/she may remain on therapy but will be ineligible for treatment with ribavirin in the event of virologic failure. If he/she is in Arm 2, therapy must be discontinued immediately and the subject will be counseled on the potential risks of exposure by the PI or designee. A discussion will occur with the medical monitor to decide whether the subject is eligible to be continued on sofosbuvir/ledipasvir alone.

Loss of graft: Defined as death or need for retransplant. Patients will be deemed a treatment failure and the intervention will be discontinued.

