10.4 Adverse Experience Reporting

In order to ensure prompt reporting of adverse events, all adverse events (as well as all related study data) must be entered into the WebDCU™ within five days of collection date. All serious adverse events (SAEs) must be reported on the WebDCU™ within 24 hours of the study site staff first being made aware of its occurrence. The site investigators are required to provide relevant information, including description of the adverse event, date/time of onset and resolution, severity and seriousness, action taken, and suspected relationship to the study treatment.

Reporting of any serious adverse event will trigger notification of the event to the DCU Project Manager (PM) and the independent Medical Safety Monitor (MSM). The MSM will conduct an independent review of each of these events to determine if it is serious, unexpected, and study treatment related.

Periodically throughout the study, the MSM will review reports on the incidence rates of all reported adverse events, whether serious or not. Should such monitoring uncover issues that may threaten subject safety (e.g. unexpectedly high rate of adverse events), the study statistician and principal investigator will prepare a report to be submitted to the DSMB for their review and further actions to be taken, if any.

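### Section 7 requires no medical-monitor decision before re-dosing after a Grade 3-4 allergic reaction or anaphylaxis that resolves within 5 days, and it is unclear which drugs and arms the two rows cover

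*Combined protocol and SAP*

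**What the plan says.** The Allergic reaction and Anaphylaxis rows are in the ribavirin table of Section 7. Modification is triggered at Grades 3 to 5 in both rows, and for allergic reaction also at the participant's request. The procedure is the same in both: "Intervention can be withheld for up to 5 days. If there is no resolution, the case will be discussed with the medical monitor", after which the intervention may be discontinued. Permanent discontinuation is mandatory only at Grade 5.

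Grade 3 anaphylaxis is described as "Symptomatic bronchospasm, with or without urticarial; parenteral intervention indicated; allergy-related edema/angioedema; hypotension". Grade 4 is life-threatening in both rows and has the same procedure as Grade 3.

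Section 8 refers back to these tables: "The intervention will be withheld/discontinued for specific grades of adverse effects as detailed in section 7". It adds no rule of its own on hypersensitivity.

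The first table in Section 7, headed "SOFOBUVIR/LEDIPASVIR OR RIBAVIRIN (ADVERSE EVENTS IN COMMON", lists events shared by the two drugs. It has ten rows, and neither allergic reaction nor anaphylaxis is among them.

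**The concern.** The trigger for involving the medical monitor is persistence of the event. That suits headache or myalgia, where a symptom that will not settle is the problem. In a severe allergic reaction the main hazard is re-exposure after recovery. The rows escalate the event that does not resolve and are silent on the event that does, which is when the question of the next dose arises. Grade 3 irritability, described as "Severe abnormal or excessive response; limiting self care ADL; inconsolable", has the same hold-and-discuss procedure, which suggests stock wording not adapted to the hazard.

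At stake is the safety of a subject who has had a severe or life-threatening reaction. In a multi-center trial it also matters that sites act alike in that situation. If the table heading limits the rows to ribavirin, a reaction to sofosbuvir/ledipasvir, the only study drug in Arm 1, would have no stated procedure.

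**Working it through.** No formula or planned figure is involved. The check follows a subject with a Grade 3 or 4 reaction that resolves within 5 days, and asks at each place in the protocol whether a decision is required before the next dose.

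1. **Section 7, the two rows.** The discussion depends on non-resolution, so it is not triggered. The mandatory stop applies only to death, so it is not triggered either. The hold itself is worded as something that *can* be done.
2. **Section 8, opening sentence.** Here the verb is *will*, so a mandatory hold may be intended. Even on that reading, the sentence governs the hold and not the restart.
3. **Section 10.4.** A serious adverse event must be entered "within 24 hours of the study site staff first being made aware of its occurrence", resolved or not, and entry notifies the independent Medical Safety Monitor. That review settles seriousness, expectedness and relatedness. It is not made a condition of the next dose. An event not reported as serious is entered within five days and reaches this monitor through periodic review.
4. **Section 6.2.3.** A visit within 72 hours is set for a subject who ends the intervention early. It is not a check before restarting after a hold, and its general aim is to encourage resumption, with no exception for hypersensitivity.
5. **Section 4.2, exclusions e and p.** Known allergy to either component of the fixed-dose tablet, or allergy to or intolerance of ribavirin, bars entry. These criteria apply only at entry and have no on-treatment counterpart.

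None of the five requires a decision before re-dosing once the event has resolved.

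The protocol does write firmer rules where it wants them. The anemia row says "Grade 3-5: ribavirin will be permanently discontinued" and the hemolysis row says "Grade 3-5: intervention will be permanently discontinued". The two differ: the anemia rule stops ribavirin only and keeps the subject on the rest of the regimen. For pregnancy in Arm 2, Section 8 requires a medical-monitor discussion, resolved or not, on whether sofosbuvir/ledipasvir may continue alone.

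**Coverage.** Two readings are open:

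- *The heading governs.* The rows concern ribavirin, hence Arm 2. Sofosbuvir/ledipasvir and Arm 1 then have no allergy procedure, because the common table has no such row.
- *The word intervention governs.* Section 5 uses it for both drugs and Section 6.2.2 for every randomized subject. The rows then cover both arms.

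The anemia row separates ribavirin from the study intervention, and the chronic kidney disease row names each drug. The two allergy rows do neither, so the text does not settle the matter.

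**Scale for the outcome.** Section 3 plans 25 subjects per arm, and Section 9.4.2 analyzes all randomized subjects as assigned. One subject who stops and then fails changes an arm's SVR12 by 1/25 = 4 percentage points.

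**The case against.** The strongest reply is that the rows are permissive. They do not direct rechallenge, an investigator may stop a drug at any time, and the allergy exclusions show that the protocol does not mean to dose subjects with known allergy. All of this stands. A reader might infer that the protocol calls for re-dosing after anaphylaxis, or that nobody independent hears of a resolved event. The documents support neither: any reaction reported as serious goes to the Medical Safety Monitor whether or not it has resolved. The protocol does not say whether that role is the medical monitor of Section 7. What survives is narrower: neither role is required to decide before the next dose.

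A second reply is that the contrast with anemia and hemolysis is selective. Hepatic failure, pancreatitis, dyspnea and depression also have life-threatening grades and use the same hold-and-discuss wording. That is correct, and the contrast shows only that a firmer rule was available. The case for the two allergy rows rests on the re-exposure hazard, not on their being the only lenient rows.

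A third reply is that Section 7 covers common or expected events, so the ribavirin heading may mark where an event is expected without limiting the action. This is a fair reading. It is why Arm 1 cannot be said to lack cover; the point is ambiguity only.

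**Conclusion.** The point holds as a narrow safety gap that should be fixed. After a Grade 3-4 allergic reaction or anaphylaxis that resolves within 5 days, no medical-monitor decision is required before re-dosing, and the drugs and arms covered by the two rows are unclear.

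Its size cannot be put as a rate, because the documents give no frequency for these events. Counting how many row-grades carry a mandatory stop would only restate the wording and would not measure risk. Nor do the documents support calling the effect on SVR12 negligible: with 25 per arm, a single failure is 4 percentage points.

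The conclusion assumes that the Section 10.4 review is limited to the classification described there, and that no document outside this protocol, such as the manual of procedures, adds a clearance step.

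**What to change.** Replace the procedure text for Grades 3-4 in both rows with:

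> *Grade 3-4: withhold the suspected study drug(s) at once. No re-dosing, whether or not the event has resolved, until the case has been discussed with the medical monitor, who decides with the investigator whether each drug is restarted or permanently discontinued. Anaphylaxis judged related to a study drug by the investigator and medical monitor: permanently discontinue that drug.*

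State that both rows apply to sofosbuvir/ledipasvir and to ribavirin in both arms, for example by moving them to the common table. If only ribavirin is suspected in Arm 2, let the medical monitor decide whether sofosbuvir/ledipasvir continues alone, as Section 8 already does for pregnancy.

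The automatic permanent stop is confined to related anaphylaxis. A Grade 3 allergic reaction may qualify merely by being slow to respond to symptomatic treatment, so an automatic stop for every related one would go beyond the gap.

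The cost is two reworded rows, one monitor contact per event with no added visit, and possibly some missed doses while the cause is established. A subject with related anaphylaxis to sofosbuvir/ledipasvir loses the backbone of both regimens, which may cost that subject the response.

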8. CRITERIA FOR INTERVENTION DISCONTINUATION

The intervention will be withheld/discontinued for specific grades of adverse effects as detailed in section 7. Additionally, the intervention will be discontinued if the subject meets criteria for the following reasons:

Virologic failure, defined as:

Breakthrough: HCV RNA \geq LLOQ after having previously had HCV RNA $<$ LLOQ, while on treatment, confirmed with 2 consecutive values (note: second confirmation value can be posttreatment), or last available on-treatment measurement with no subsequent follow up values, OR

Rebound: > 1 log₁₀IU/mL increase in HCV RNA from nadir while on treatment, confirmed with 2 consecutive values (note: second confirmation value can be post-treatment), or last available on-treatment measurement with no subsequent follow up values, OR

Nonresponse: HCV RNA persistently \geq LLOQ through 8 weeks of treatment, OR

Relapse: HCV RNA \geq LLOQ during the posttreatment period having achieved HCV RNA $<$ LLOQ at end of treatment, confirmed with 2 consecutive values or last available posttreatment measurement

Pregnancy: If a woman becomes pregnant or a male's female partner becomes pregnant while on-study, the subject will be required to instruct investigators immediately. If he/she is in Arm 1, he/she may remain on therapy but will be ineligible for treatment with ribavirin in the event of virologic failure. If he/she is in Arm 2, therapy must be discontinued immediately and the subject will be counseled on the potential risks of exposure by the PI or designee. A discussion will occur with the medical monitor to decide whether the subject is eligible to be continued on sofosbuvir/ledipasvir alone.

Loss of graft: Defined as death or need for retransplant. Patients will be deemed a treatment failure and the intervention will be discontinued.

9. STATISTICAL CONSIDERATIONS

9.1 General Design Issues

This is a multi-center, prospective, randomized, open-label, intent-to-treat pilot study.

The primary objective is to estimate the effect that LDV/SOF for 12 weeks will have on SVR12 compared to LDV/SOF plus ribavirin for 12 weeks.

9.2 Outcomes

9.2.1 Primary outcome - Treatment efficacy, defined as the proportion of subjects achieving sustained virologic response 12 (SVR12) weeks after completing the antiviral regimen

9.2.2 Secondary outcomes - Secondary endpoints include the proportion of subjects achieving clearance of viremia during therapy, at the end of therapy, week 4 and 24 SVR (week 4, week 8, EOT, SVR4, SVR24).

9.2.3 Safety outcomes - Overall safety and tolerability of each regimen will be estimated by measuring the incidence of adverse drug reactions and the development of medication intolerance requiring dose reduction, temporary withdrawal, or removal of the study drug(s), incidence of the need for supportive medications (erythropoietins, colony-stimulating factors), incidence of intolerance requiring dose reduction, temporary withdrawal, or removal of immunosuppressants, overall and opportunistic infections, biopsy-proven rejection rates, death, and graft loss. Other safety outcomes include virologic mutations based on NS5A and NS5B viral substitutions at baseline and in the event of virologic failure.

9.3 Sample Size Estimation for the Primary Outcome

For a definitive trial, if we assume an efficacy rate of 95% with an acceptable noninferiority margin of 10%, 75 subjects would be needed in each arm to provide an alpha level of 0.05 with 80% power to demonstrate noninferiority. Assuming a 10% dropout rate (indicating randomization, but failure to receive a dose of study medication), 85 subjects would need to be randomized in each arm. In this pilot study of 50 subjects, we will be able to obtain estimates of these rates for the two groups for use in the future definitive trial.

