6.2 Timing of Evaluations

6.2.1 Pre-Randomization Evaluations

These evaluations occur prior to the subject receiving any study interventions.

Baseline

The evaluations listed under the Baseline visit may be performed up to 14 days prior to randomization, with the exception of the pregnancy test, which must be performed within 48 hours of randomization. Additionally, HCV PCRs may be performed up to 30 days prior to randomization, provided that it was performed after the liver transplant.

Once the subject has been successfully screened and accepted for randomization, randomization must be complete within 48 hours. All subjects randomized will be included in the intent-to-treat analysis.

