6.2.2 Intervention and Evaluations

Once the subject has been successfully randomized, the intervention should be initiated upon that day, but must be initiated within 5 days in case of extenuating circumstances.

Study evaluations must take place within the time window indicated on the Schedule of Evaluations (Section 6.1).

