6.2.3 Intervention Discontinuation Evaluations

At the scheduled time of intervention discontinuation (EOT, last date of study medication), the following evaluations must be completed: HCV PCR and HCV viral substitutions (in the event of virologic failure)

If a subject prematurely terminates study intervention, a visit will be scheduled with the Principal-Investigator (PI) or designee within 72 hours to evaluate the reason for early termination. The PI or designee will attempt to resolve any issues leading to early termination and encourage the subject to resume study intervention as soon as possible. It will be clarified whether they are terminating from all components of the trial or only from the primary intervention component of the trial. If possible, the subjects will be encouraged to continue to be followed and evaluated according to the Schedule of Evaluations (Section 6.1) even if they no longer wish to receive study treatment.

Subjects that discontinue intervention due to virologic failure will be withdrawn from the study and deemed a treatment failure. These subjects may receive alternative treatment at

the investigator's discretion. SOF/LDV will be supplied upon request and RBV will be reimbursed by Gilead Sciences, Inc for up to 24 weeks if requested.

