9.4 Statistical Evaluation of Primary Endpoint

9.4.1 Statistical Hypotheses:

The specific null and alternative hypotheses for comparing these two treatments in a non-inferiority design are: $H_0: \pi_{LDV/SOF+ribavirin} - \pi_{LDV/SOF} = \delta_0$ and $H_A: \pi_{LDV/SOF+ribavirin} - \pi_{LDV/SOF} < \delta_0$ (non-inferior) where $\delta_0 = 0.10$. where $\pi_{LDV/SOF+ribavirin}$ (assumed to be 95%) represents the proportion with a successful outcome due to treatment with LDV/SOF plus ribavirin for 12 weeks and $\pi_{LDV/SOF}$ represents the proportion of a successful outcome due to treatment with LDV/SOF for 12 weeks.

9.4.2 Efficacy Analysis:

Although there is insufficient power to conduct any formal statistical analyses, preliminary estimates of effects for treatment comparisons will be intent-to-treat, where all randomized subjects will be included in the analysis and each subject will be included in the treatment to which they were randomized.

Baseline demographics and clinical outcomes will be presented by treatment. Estimates of the differences between these, along with 95% confidence intervals, will be generated. The primary outcome of proportion of subjects with success (defined as the proportion of subjects achieving sustained virologic response 12 (SVR12) weeks after completing the antiviral regimen) as well as estimates of all secondary outcomes for each treatment will be reported along with 95% confidence intervals.

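### Does the future trial's 85 per arm lose its power because never-dosed subjects stay in the intent-to-treat set?

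*Combined protocol and SAP*

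**What the plan says.** Section 9.3 describes a definitive trial that would follow this pilot. With 95% efficacy, a 10-point non-inferiority margin, alpha 0.05 and 80% power, it gives 75 per arm. It then goes to 85: "Assuming a 10% dropout rate (indicating randomization, but failure to receive a dose of study medication". Of the present 50 subjects it says only that "we will be able to obtain estimates of these rates for the two groups for use in the future definitive trial".

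For the pilot, section 9.4.2 first states that power is too low for formal analysis. It then sets an intent-to-treat estimate in which "all randomized subjects will be included in the analysis and each subject will be included in the treatment to which they were randomized". Section 6.2.1 agrees: "All subjects randomized will be included in the intent-to-treat analysis".

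The primary outcome in section 9.2.1 is "the proportion of subjects achieving sustained virologic response 12 (SVR12) weeks after completing the antiviral regimen". Treatment failure is assigned by name in two places. Section 6.2.3 covers virologic failure ("Subjects that discontinue intervention due to virologic failure will be withdrawn from the study and deemed a treatment failure"), and section 8 covers graft loss ("Patients will be deemed a treatment failure and the intervention will be discontinued"). On starting treatment, section 6.2.2 asks for the day of randomization and otherwise says it "must be initiated within 5 days in case of extenuating circumstances".

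**The concern.** Dividing a sample size by one minus the dropout rate replaces subjects who disappear from the analysis. Under intent-to-treat a never-dosed subject does not disappear: he or she stays in the denominator and, if scored as a failure, pulls the response rate down. Section 9.3 therefore seems to size by removing these subjects while section 9.4.2 analyses by keeping them.

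The pilot's purpose is to pass rates on to the next trial, so the denominator matters. A planner who took the rate among dosed subjects, used 85 per arm and then analysed all randomized subjects would run an undersized trial. A planner who took the all-randomized rate and added 10% for non-start would count non-start twice. The lack of a sentence on scoring a subject who never starts, and so has no regimen completion date, seems to leave open which rate the pilot will report.

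**Working it through.** **Inputs.** From section 9.3: response p = 0.95 in both arms, margin 0.10, power 80%, 10% never dosed, 75 and then 85 per arm. Sidedness of alpha is not stated. Assumed here, because the plan does not say: non-start is equal in both arms, and a kept non-starter counts as non-SVR12.

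**Reproducing the plan.** n = (1.960 + 0.842)² × 2p(1 − p) / 0.10².
- At p = 0.95 this gives 74.6, so 75, which matches. It corresponds to one-sided 0.025 (two-sided 0.05); one-sided 0.05 would give 59.
- 75 / 0.90 = 83.3, so 84. The stated 85 is one more and harmless.

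**Power at a fixed size.** Power = Φ(0.10 / √(2p(1 − p)/n) − 1.96).

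| Reading of the future trial | p | n analysed per arm | Power | n per arm for 80% |
|---|---|---|---|---|
| Non-starters excluded (85 × 0.90 ≈ 76) | 0.95 | 76 | 81% | 75 analysed |
| 95% already covers all randomized | 0.95 | 85 | 85% | 75 |
| Kept as failures, 10% non-start | 0.95 × 0.90 = 0.855 | 85 | 46% | 195 |
| Kept as failures, 5% non-start | 0.9025 | 85 | 59% | 139 |
| Kept as failures, 2% non-start | 0.931 | 85 | 73% | 101 |
| Kept as failures, 0.5% non-start | 0.945 | 85 | 82% | – |

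Only the 10% non-start rate comes from the plan; the lower rates show the range. Exact binomial enumeration of the 10% row gives 46.2%. The second row does not fit the plan's own inputs: with 10% never dosed and scored as failures, the all-randomized rate cannot exceed 90%. At 90%, power is 58% and 142 per arm are needed.

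**Double counting.** Inflating 195 again gives 195 / 0.90 = 216.7, so 217 per arm, 22 too many.

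**Which reading fits section 9.3?** It defines dropout as never receiving a dose and inflates for it. Section 9.4.1 attaches the 95% to success attributed to twelve weeks of the ribavirin-containing treatment. Both point to a rate among treated subjects and an analysis of dosed subjects, which is the first row.

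**Is a pilot non-starter unscored?** Put sections 9.2.1 and 9.4.2 side by side. The numerator is subjects who achieve SVR12 after completing the regimen; the denominator is everyone randomized. A subject who never starts cannot enter the numerator and cannot leave the denominator, so the result is non-SVR12. The failure rules in sections 6.2.3 and 8 deal with virologic failure and graft loss, and their silence on non-starters does not undo this.

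**What one non-starter does to the pilot's rate.** Suppose 1 of 25 is never dosed and 23 reach SVR12.
- All randomized: 23/25 = 92.0% (Wilson 95% CI 75.0% to 97.8%), which gives 116 per arm in the formula.
- Dosed: 23/24 = 95.8% (CI 79.8% to 99.3%), which gives 63 per arm.
- The limits of the first interval, 75.0% and 97.8%, give 295 and 34 per arm.

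The choice of denominator moves the answer by 53 per arm; sampling error alone spans 261.

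**The case for a change.** The best argument for a change is that rates are the pilot's deliverable. Section 9.3 foresees up to one subject in ten never being dosed, and no dosed, modified intent-to-treat or per-protocol efficacy set is defined anywhere. A single reclassified subject moves the derived size from 116 to 63 per arm. Sampling error at 25 per arm cannot be removed, whereas ambiguity about the denominator can, for a few sentences and one table.

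Part of this stands. Section 9.3 does not name the analysis set behind its 85, and a later trial that combined 85 per arm with an all-randomized analysis and 10% non-start would be badly underpowered.

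The rest does not carry. The two rules said to conflict belong to two different trials, one of which has no protocol yet, and that trial need not copy the pilot's analysis set. The harm requires its planners to use a rate without checking its denominator, although the pilot will hold the randomized count, the dosed count and the SVR12 count in each arm. Section 6.2.2's short window for starting treatment also suggests few non-starters among 50, though the plan gives no expected number.

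**Conclusion.** No change to the plan is needed. The figure 75 reproduces, and 85 is adequate (about 81% power) on the reading that best fits sections 9.3 and 9.4.1: 95% among dosed subjects, in a trial that analyses dosed subjects. The drop to 46% power, with 195 per arm needed, is real arithmetic. It rests on three conditions the plan does not set for the later trial: an all-randomized analysis, non-starters scored as failures, and 10% non-start in each arm. Unequal non-start would change it sharply. With 5% in the ribavirin arm and 15% in the other, power would be about 3%; with the reverse, about 95%.

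The pilot's size, its estimates and their confidence intervals depend on none of this. Followed as written, it yields an all-randomized SVR12 proportion in which a non-starter counts as a non-success. What remains is an unstated detail about a hypothetical trial, which its planners would settle when they write its protocol. Adding words now would record a scoring rule the text already implies and tabulate counts the pilot will have anyway.
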